8.2. Analysis Plan

Demographic characteristics of the sample (income level, age, gender, race/ethnicity, educational level) will be provided using descriptive statistics to describe the overall sample and by group to ensure that randomization was effective. Distribution of variables will be determined prior to further statistical analysis. SAS software (80) will be used for all analyses.

To address the primary aims, mixed models will be used. The first aim is to determine the direct and interactive effects of genetic risk information incorporated with standard CHD/T2D risk counseling and a health coaching intervention for CHD/T2D on behavior change (diet, physical activity) in AF primary care patients over 12 months. The goals of the statistical analysis will be to quantify: (1) the extent to which genetic risk counseling influences the trajectory of change in physical activity and diet measures from baseline to 3, 6, and 12 months; and (2) the extent to which the genetic risk information augments the trajectory of the effects of health coaching on diet and physical activity measures over the same time period. We will fit two general linear mixed models to these data (81), with

physical activity and diet measures at each of the five points in time. For either model, there will be three independent variables: genetic risk information (G) with values of 1 or 0, health coaching (HC), also with values of 1 or 0, and time since randomization, with values of 0, 3, 6, and 12 months. Within the context of the linear mixed model, we should observe a statistically significant three way interaction of time by genetic information by health coaching. The particular type of longitudinal model selected for analysis will depend upon preliminary analyses of the data. For example, a subject specific (also called hierarchical) model with random intercept and slope assumes that within subject variances increase or decrease over time. A model hypothesizing only a random intercept does not assume that within subject variances show this pattern. Another consideration will be the extent of missing data; some longitudinal models are better than others at handling missing data.

The second part of the primary analysis will determine the direct and interactive effects of genetic risk information incorporated with standard CHD/T2D risk counseling and a health coaching intervention for CHD/T2D on metabolic outcomes (fasting blood glucose, SBP, BMI, waist circumference, LDL, triglycerides, total cholesterol) over 12 months. The statistical analysis will be the same as above except that the dependent variables will be fasting blood glucose, SBP, BMI, waist circumference, LDL, triglycerides, and total cholesterol.

To address Aim 2, we will examine the mediating effects of level of CHD/T2D genetic risk (number of risk alleles) and consequent reclassification of FRS in the case of CHD risk (decreased, neutral, or increased) on behavior change (diet, physical activity) at 6 months. The goal of this analysis is to quantify the extent to which subgroups of patients exhibit different levels of change in diet and physical activity behavior at 6 months post randomization depending on reclassification of FRS and T2D risk level. We also want to know if the differences depend on whether or not the genetic results were delivered in the context of health coaching. For these analyses, we will use results from only the two groups of patients randomized to receive genetic testing (n=200). Because we will have only two points in time, we will use the simpler linear regression model, with the dependent variable being either diet or physical activity collected at 6 months post randomization. There will be six independent variables: the outcome measured at baseline (a covariate), the results of the genetic testing (entered as two dummy coded variables), a dummy coded variable to indicate the presence or absence of health coaching, and two dummy coded variables representing the interaction of health coaching and the results of genetic testing. We are particularly interested in comparing the diet and physical activity changes of patients whose genetic test results move their Framingham risk or T2D levels either up or down (based on number of higher-risk alleles) to those whose genetic

results do not. In our regression analysis, this comparison will be facilitated by creating two dummy coded variables; dummy 1 will be 1 if the patient has ‘low’ risk based on number of risk alleles and zero otherwise. Dummy 2 will be 1 for patients with ‘high’ risk based on number of risk alleles and zero otherwise. When group membership is coded in this way, the regression coefficients (parameters) fit to the data represent differences in adjusted group means. “Adjusted” refers to group differences on outcome measures obtained at 6 months, while statistically eliminating any differences between groups on outcomes at baseline. Thus, the regression coefficient for dummy 1 will reflect the differences in average adjusted outcome at 6 months between patients whose genetics results shifted their risk down and patients whose results did not affect their risk. Similarly, the regression coefficient for dummy 2 will reflect differences in adjusted outcome means comparing patients whose risk shifted up to those whose risk was unaffected by their genetic test results. The interaction components of this model will allow us to assess whether or not these comparisons significantly differ depending upon whether or not the patient received health coaching.

Secondary analyses will examine the mediating effects of perceived CHD/T2D risk, self-efficacy, worry, patient activation and readiness for change on the effects of genetic risk information on diet and physical activity at 6 months post randomization. The analytic strategy will be to determine the extent to which genetic risk treatment effects on diet and physical activity occur subsequent to treatment effects on perceived CHD/T2D risk, self-efficacy, worry, patient activation and readiness for change. For example, one set of analyses will estimate the direct relationship between genetic risk counseling and changes in physical activity at 6 months (independent of evaluation of the effects of treatment on perceived risk). Additionally, the extent to which genetic risk counseling influences perceived risk at 6 weeks and 3 months post randomization, *which in turn affects behavior change at 6 months*, will be assessed. This analysis will be repeated using diet as the dependent variable. Then both will be repeated using self-efficacy, worry, patient activation and readiness for change as mediators. In each analysis, mediation will be estimated via a series of linear regressions. Mediation will be *tested statistically* by examining the empirically generated sampling distribution of the parameters involved in the mediational hypothesis: the effect of treatment on the mediators at 6 weeks and 3 months, the effect of the mediators at 3 months on the dependent variable at 6 months, and the product of these effects. We will use bootstrapped sampling distributions of the parameters involved in each mediational hypothesis. Recent work supports this method rather than the more traditional Sobel tests, especially with smaller samples.

9. Protection of Human Subjects

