3.3. Exclusion Criteria

A patient will **not** be eligible for inclusion in this study if any of the following criteria apply:

1. Projected deployment in the upcoming 6 months ;
2. Diagnosed T2D;
3. Diagnosed CHD (MI, or documented CHD);
4. Inability to ambulate or participate in physical activity;
5. Serious chronic disease related complications or conditions that could significantly affect study outcomes [currently treated cancer, renal failure, cardiovascular accident (CVA) with residual effects on functioning];
6. Current participation in another research study ;
7. Spouse, partner or other household member already participating in this study protocol.

The cardio-metabolic risk factors used for inclusion are those identified by the FRS and national guidelines (National Cholesterol Education Program, AHA, ADA). Because we are targeting those at risk for CHD and/or T2D, participants must have at least one factor in the risk ranges listed. Patients with diagnosed CHD or T2D are excluded because this study is targeted toward prevention of these conditions in those at risk. Those with physical activity limitations or other serious co-morbidities are excluded due to potential effects on participation and study outcomes. The age limit of 18-65 years was designated as much of the risk of T2D or CHD in older adults is due to

age; not modifiable risk factors. Therefore, many intervention studies aimed at risk reduction limit participation to those at age 65 or younger.

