4. SRA+HC+GRC

The primary outcomes of this study are behavioral (diet and exercise/fitness), collected at 6 weeks, and 3, 6 and 12 months. At 12 months, clinical outcomes will be measured at the clinic (blood pressure, weight, and waist circumference). And at 12 months, clinical outcomes will be documented from the electronic medical record (EMR) (glucose, lipid panel, change in risk status, AF fitness scores*) from the subjects' annual visit results.

*Note: AF fitness scores are provided following required annual fitness evaluations for all ADAF only (not beneficiaries, retirees) and are age and gender based. The variables considered with points for level of performance in each category are: Cardiorespiratory endurance (run time); Body composition (abdominal circumference); and Muscle fitness (push-ups). A composite score derived from adding points in all categories must be >75. Ranges are defined for Unsatisfactory; Satisfactory and Excellent.

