5.1. Expected Enrollment

Total of two hundred fifty (250) subjects will be enrolled in two primary care clinics, at two sites as follows:

1. David Grant Medical Center ,Travis Air Force Base, Solano, California
2. McClellan Outpatient Satellite Clinic, McClellan Air Force Base, Sacramento County, CA

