5.2. Recruitment

Ascertainment of potential subjects will be obtained by physician referral, patient self-referral or EMR chart review (Appendix I. and J.) The study coordinator will mail a letter, signed by the subjects' primary care physician, to those individuals identified by EMR chart review, introducing the study. After 2 weeks, the CRC will follow-up with a brief phone call to assess subjects' interest in study participation. (Appendix G. and H.). If the potential subject is interested in participation, consent and baseline visit will be scheduled. Patients identified by physician referral may be consented at time of physician referral or contacted later by phone to arrange consent and/or baseline visits. For

Genetic Risk Testing and Health Coaching for CHD and T2D

Duke IRB# Pro00039569 NCT01884545

self-referred patients the initial phone conversation will be followed by consent/baseline visit in the clinic. Since a major target population for this study is ADAF, beneficiaries, and retiree patients, we will be placing flyers/advertisements/recruitment staff in locations on base to reach this audience including gymnasiums, annual fitness evaluation centers and annual exam clinics on base.

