4. SRA+HC+GRC

Random assignments will be generated using a standard random number generator with uniform distribution to the four groups by the Clinical Genomics Study Unit (CGSU) data manager. The research staff (CRC at site) will use this randomization schema to inform participants of their group assignment.

Follow up visits:

6-week and 3-month – At 6 weeks and 3 months after the baseline visit, participants will be asked to complete selected surveys online (Table 1). The 6 week survey must be completed after the counseling visit and before Health Coaching begins.

6-month – Six months from the baseline visit, participants will return to the clinic to have weight, BP and waist circumference measured (same procedures as baseline visit). Medications will be reviewed and AE's assessed.

Female subjects will be asked if they are currently pregnant and this will be documented.

They will also complete the required surveys as listed, either before their scheduled visit or during their visit at the clinic.

12-month- Twelve months from the baseline visit, participants will return to the clinic for a final visit to have weight, BP and waist circumference measured (same procedures as baseline visit). Medications will be reviewed and AE's assessed.

Lab values from the EMR will be documented for fasting glucose, TC, HDL, LDL, TRIG CRC will check in EMR prior to each subject's 12-month visit. If lab values as stated above are not available from the last 6 months of study participation , then a lipid panel (TC, HDL, LDL, TRIG) and either a FBG or HbA1c will be ordered. Female subjects will be asked if they are currently pregnant and this will be documented.

They will also complete the required surveys as listed, either before their scheduled visit or during their visit at the clinic.

Window of ±one week were allowed for all follow up visits. In order to maximize power and considering

Genetic Risk Testing and Health Coaching for CHD and T2D

Duke IRB# Pro00039569 NCT01884545

recent findings on the stability of metabolic clinical markers absent behavior change, statistical analyses will employ extended inclusion windows for study time-points. Statistical analyses will include: +/-3 weeks for the 6 week survey, +/-7 weeks for the 3 month survey, and +/-11 weeks for the 12 month survey.

Table 1.

STUDY VISITS	GROUP 1	GROUP 2	GROUP 3	GROUP 4

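### The primary models in 8.2 leave out site, active-duty status, age and sex after unstratified assignment, which gives up some precision on the pooled coaching-by-genetics contrast but not on the by-time tests

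*Combined protocol and SAP*

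**What the plan says.** Under Randomization in section 5.3.1: "Random assignments will be generated using a standard random number generator with uniform distribution to the four groups". No blocks or strata are described. Section 5.1 states: "Total of two hundred fifty (250) subjects will be enrolled in two primary care clinics, at two sites as follows". Section 5.2 names active-duty members, beneficiaries and retirees as the target population, and section 3.2 admits ages 18 to 65.

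For the diet and activity models, 8.2 says "For either model, there will be three independent variables" and lists G, HC and time. It applies the same analysis to glucose, SBP, BMI, waist circumference and lipids. Age and gender have only a descriptive role: "Demographic characteristics of the sample (income level, age, gender, race/ethnicity, educational level) will be provided using descriptive statistics". Site and duty status enter no model. What 8.2 leaves open is the longitudinal form: "The particular type of longitudinal model selected for analysis will depend upon preliminary analyses of the data". Its examples concern random effects, and it then mentions missing data.

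Section 5.3.1 says that pregnancy is recorded so that confounding can be handled in the analysis. Section 8.2 has no such term.

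After the sample-size cut, section 8.1 keeps two targets, joined by and/or: the HC-by-time and G-by-time interactions, and the HC-by-G interaction without time.

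**The concern.** Activity, diet, BMI, blood pressure and lipids can be expected to differ by age, sex and duty status, and perhaps by site. Only active-duty members face the annual fitness evaluation. With none of these factors in the model, the stable differences between people that they explain stay in the error of any contrast that compares average levels. A chance imbalance in them is also left uncorrected. Recruitment was slow and the sample was cut from a planned 460 to a minimum of 212, so precision that needs little or no extra data collection is worth having. The pregnancy remark shows that some adjustment was intended. Without a rule in 8.2, any covariates would be chosen after the data are seen, or not at all.

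**Working it through.** **Inputs from section 8.1.** Type I error .025 per primary analysis (two-sided assumed); within-person correlation 0.35; 44 per group (176 total) for power .80 on pooled HC by G; 15% attrition; minimum sample 212; five time points. Outcome SD is taken as 1 with compound symmetry. The share *r* of between-person variance explained by the four covariates is not in the documents; I use 5% to 30%.

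**The plan's own figures.** 176/0.85 = 207.1, or 208 rounded up, within 3% of 212; 180/0.85 = 211.8 gives 212. In reverse, 212 × 0.85 = 180 completers, 45 per group. For the G-by-time test (pattern 2, 4-df F test) I get power 0.769 at 43 per group and 0.834 at 49, against the stated .80 and .85. Agreement is approximate.

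**Pooled HC by G.**
- Variance of a person's mean over five times: v = 0.35 + 0.65/5 = 0.48.
- Variance of the interaction contrast (four cell means): 4v/n, with n per group.
- Contrast giving power .80 at n = 44: (2.241 + 0.842) × √(4 × 0.48/44) = 3.083 × 0.2089 = 0.644 SD. It is back-solved because the pattern means for this interaction are not in the text.
- With covariates: v(r) = 0.35(1 − r) + 0.13. Power at n = 45 is Φ(0.644/√(4v(r)/45) − 2.241).

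| r (assumed) | v(r) | SE reduction | Power, 45 per group | Total N for .80 |
|---|---|---|---|---|
| 0 | 0.480 | – | 0.81 | 176 |
| 5% | 0.4625 | 1.8% | 0.825 | 172 |
| 10% | 0.445 | 3.7% | 0.84 | 164 |
| 20% | 0.410 | 7.6% | 0.87 | 152 |
| 30% | 0.375 | 11.6% | 0.90 | 140 |

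Section 8.2 lists four times (0, 3, 6 and 12 months). Then v = 0.35 + 0.65/4 = 0.5125, and the SE reduction is 1 − √(0.495/0.5125) = 1.7% at r = 5% and 1 − √(0.4075/0.5125) = 10.8% at r = 30%. The conclusion is unchanged.

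**By-time interactions.** These are within-person contrasts, so covariates that do not vary over time cancel. In simulated fits with four such covariates as main effects, the SE of G by 6 months was 0.1572 with and without them. With 15% dropout it was 0.1636 without and 0.1634 with.

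**Chance imbalance.** Assume 250 randomised and 50% active duty. Each factorial contrast (HC, G, HC by G) sets about 125 people against 125. The SD of the gap in active-duty share is √(0.25 × 2/125) = 0.0632. A gap of 10 points or more is 1.58 SD, probability about 11%; 15 points or more is 2.37 SD, about 2%. Simulation with 200,000 draws agrees.

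**The case against.** The strongest reply is that 8.2 is written about trajectories, and on the by-time tests these covariates gain nothing as main effects. That stands, and it confines the point to average-level contrasts. Labs are taken only at baseline and 12 months, so for lipids and glucose the natural effect is a change, where main effects cancel again. A gain there would need covariate-by-time terms.

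The size is also undocumented, and it would be smaller if the analysis conditioned on the baseline outcome. With the mean of three follow-ups adjusted for baseline and b = 0.35(1 − r), the variance is b + 0.65/3 − b²/(b + 0.65). This is 0.444 at r = 0, 0.437 at 5% and 0.395 at 30%, an SE reduction of about 1% to 6%. The primary models in 8.2 treat baseline as a response at time 0 and not as a covariate, so the larger range applies to the pooled contrast as written.

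A reader might infer more than the documents support:
- *Bias or false positives.* Simple randomisation protects against both, with or without covariates.
- *Frequent serious imbalance.* The largest gap among all six pairs of groups reaches 15 points in 34% of draws, but that is not the comparison a 2×2 analysis tests. The figure for a given contrast is about 2%.
- *Higher active-duty dropout.* Section 3.3 excludes only "Projected deployment in the upcoming 6 months" in a 12-month trial, but no dropout figure by duty status is given.
- *A deliberate decision against all adjustment.* The pregnancy remark in 5.3.1 points the other way.

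**Conclusion.** The point holds as a limited matter of efficiency. The primary models omit baseline factors that are available and likely to be prognostic, and assignment does not balance them. The loss falls on the pooled HC-by-G interaction and other average-level contrasts: about 2% to 12% of the standard error, or power of about 0.81 against 0.825 to 0.90 at 180 completers. This rests on the assumed 5% to 30% of between-person variance, the plan's correlation of 0.35, compound symmetry and the back-solved contrast of 0.644 SD. There is essentially no loss on HC by time or G by time. A gap of 10 points or more in active-duty share on a given factorial contrast has a chance of about 11%, if half the sample is active duty.

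**What to change.** Change 8.2 so that the diet, activity and metabolic outcome models include site, active-duty status (yes/no), age and sex as pre-specified fixed baseline covariates, whatever balance is observed. State whether any of them also enters by time.

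Use the two-level duty variable: it follows from which participants have fitness-score records, whereas a three-level split into active duty, beneficiary and retiree is not shown to be collected. Omit duty status from any model of the AF fitness score, where it is constant.

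Reconcile the pregnancy adjustment in 5.3.1 with 8.2: name the term or withdraw the statement. Pregnancy recorded at 6 and 12 months arises after randomisation and is not a baseline covariate.

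Cost: about 4 degrees of freedom (one per covariate, with age linear) and SAP wording.

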8.1. Sample Size/Power Calculation

The objective of the power analysis was to determine the minimum sample size needed to reject the null hypothesis that the three-way genetic information by health coaching by time interaction was equal to zero in the context of a longitudinal general linear mixed model. The model was assumed to have two levels of genetic information (present or absent), two levels of health coaching (present or absent), and five levels of time (0, 1.5, 3, 6 and 12 months after randomization). In producing the required sample-size estimates, we further assumed that each of the four group means over time would take on standardized mean values. The type I error rate was set to be no greater than .025 as there will be two primary analyses. Controlling each one at no greater than .025 controls the overall experiment type I error rate to be no greater than .05. Calculations indicated that with a sample size of 99 subjects per group, or 396 total, the power to reject the null hypothesis concerning the three-way interaction was .80. Assuming an attrition rate of at most 15% and the current pilot diabetes study attrition of 11%, over the 12 month time period we calculated a possible required sample size of $(396/.86)=460$ to attain the target sample of 400. Sample size calculations are not provided for detecting the direct effects or interactive effects of the two interventions pooled over time, primarily because we expect the genetic information by health coaching interaction to change over time, as reflected in the three-way interaction.

Due to delayed/slow recruitment the sample size is revised as following (modification approved in contract amendment):

A reduced sample size, but collecting data out to 12 months as planned:

- a. Coming from the stance that we want to preserve as much of the original thinking behind the power analysis as possible, we eliminated the calculation and testing of the three way

interaction which was originally planned. This three way interaction said that the interaction of Health Coaching and genetic testing peaks at 6 months. The idea was that there was a synergy between genetic testing and health coaching which would push health behavior means for the subjects receiving both components to far greater than the individual effects of either one. Elimination of the three way interaction takes away our ability to say when this occurs (time).

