Pattern	Type I error rate	Power	Within Person Correlation	Sample Size per Group	Total Sample Size
1	.025	.80	.350	25	100
1	.025	.85	.350	27	108
2	.025	.80	.350	44	176
2	.025	.85	.350	49	196
3	.025	.80	.350	56	224
3	.025	.85	.350	63	252

- b. Means for the four groups pooled across time showing JUST the coaching by genetics testing interaction for each pattern.
- c. Examining the health coaching by time and the genetic testing by time interactions. Assuming the same means over time for pattern 2, the means for the two interactions would be as shown in the two tables immediately below.

Health coaching by time interaction for pattern 2

	NO HC	HC
0	0.05	0.05
1.2	0.15	0.5
3	0.275	0.95
6	0.125	1.5
12	0.05	0.85

Genetic testing by time interaction for pattern 2

	No Genetics	Genetics
0	0.05	0.05
1.2	0.225	0.425
3	0.425	0.8

6	0.525	1.1
12	0.225	0.675

d. Results of power calculations when the three way interaction for the groups, as well as the three way interaction for time by health coaching by genetic testing are eliminated. These are the power for detecting the interaction which is the smallest (the genetic testing one).

Pattern	Type I error rate	Power	Within Person Correlation	Sample Size per Group	Total Sample Size
2	.025	.80	.350	43	172
2	.025	.85	.350	49	196

While we will have lost the power to examine a 3-way interaction (health coaching by genetic risk testing by time), with the participants, we will still be able to:

- 1) Examine 2 way interaction effects of health coaching by time and genetic risk testing by time (estimated minimum sample needed 172-196);
AND/OR
- 2) Examine the 2 way interaction of health coaching and genetic risk testing (comparative effectiveness without time point considered in interaction; estimated sample needed 176-196).

Assuming an attrition rate of at most 15% the required minimum sample size is 212.

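### Cheap efficiency gain: a common baseline mean, or baseline adjustment, in the 8.2 mixed models would raise genetics-by-time power for diet and physical activity from about 0.86 to 0.99 at 53 analysed per group

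*Combined protocol and SAP*

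**What the plan says.** - **Model terms.** Section 8.2 (Analysis Plan) fits general linear mixed models to diet and physical activity with three independent variables: genetic risk information as a binary indicator, "health coaching (HC), also with values of 1 or 0, and time since randomization, with values of 0, 3, 6, and 12 months". No baseline covariate and no common baseline mean is mentioned. The type of longitudinal model is left to preliminary analyses. The examples given there concern random effects and missing data.
- **Clinical outcomes.** For glucose, SBP, BMI, waist and lipids, 8.2 states: "The statistical analysis will be the same as above except that the dependent variables will be" those measures. Table 2 schedules diet and activity at 0, 3, 6 and 12 months, and weight, waist and blood pressure at 0, 6 and 12 months.
- **Tests retained.** After the sample was reduced, section 8.1 drops the three-way interaction and keeps the ability to "Examine 2 way interaction effects of health coaching by time and genetic risk testing by time". It identifies genetics by time as the smallest of these effects and gives sample sizes for it.
- **Baseline adjustment elsewhere.** The separate 6-month regression on genetic results in 8.2 does take the baseline outcome as a covariate, with the stated purpose of "statistically eliminating any differences between groups on outcomes at baseline".
- **Randomisation.** Section 5.3.1 assigns participants to the four groups by a uniform random number generator. The pattern 2 means in 8.1 are equal at time 0 (0.05 and 0.05).

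**The concern.** When baseline is one of the outcome times and its group means are free, a group-by-time test with categorical time compares changes from baseline. Each visit contrast is the post-baseline difference minus the observed baseline difference. Under randomisation that baseline difference is zero in expectation, so subtracting it in full adds sampling noise and removes no bias. A model with a common baseline mean, or with baseline as a covariate, subtracts only the part that the within-person correlation justifies. At a correlation of .35 that is about a third of it.

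Genetics by time is the effect that sets the reduced sample size, diet and activity are primary outcomes, and recruitment was slow enough to force the reduction. What is at stake is precision that the trial could have from data it already collects.

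**Working it through.** **Inputs from the documents**
- Alpha: "The type I error rate was set to be no greater than .025 as there will be two primary analyses" (8.1).
- Scale: "each of the four group means over time would take on standardized mean values" (8.1), read as SD 1. No other SD is given.
- Time as a factor: 8.1 describes "five levels of time (0, 1.5, 3, 6 and 12 months after randomization").
- Genetics minus no genetics, pattern 2 (8.1): 0, 0.20, 0.375, 0.575 and 0.45 at the five times. For example, at 6 months 1.1 − 0.525 = 0.575.
- Correlation .350, with 43 per group for power .80 ("2 .025 .80 .350 43 172") and 49 per group for .85.
- Enrolment 250 (5.1) and attrition of at most 15% (8.1): 250 × 0.85 = 212.5, about 53 analysed per group.

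**Assumptions:** compound symmetry, and the same SD at all visits.

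**Formulas.** Each level of the genetics factor holds 2n participants (n per group), so a difference in means has covariance V/n. With T post-baseline visits, d the vector of post-baseline differences, I the identity and J the all-ones matrix:
- free baseline: V = (1 − ρ)(I + J)
- baseline constrained equal, or adjusted: V = (1 − ρ)(I + ρJ)
- noncentrality λ = n · d′V⁻¹d, which gives n[Σd² − (Σd)²/(1+T)]/(1−ρ) when free and n[Σd² − ρ(Σd)²/(1+ρT)]/(1−ρ) when constrained
- power from the noncentral F at alpha .025 with T and 4n − 4 df.

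**Step 1: the plan's own figures.** Take all five times with a free baseline: the sum of squares about the mean difference of 0.32 is 0.20175, and λ = n × 0.20175/0.65. That is 15.21 at n = 49 and 13.35 at n = 43. With 4 and 4(4n − 4) df, power is 0.834 (stated .85) and 0.769 (stated .80). A free-baseline test of trends up to cubic gives 0.87 and 0.81. A constrained baseline would give 0.98 and 0.96 at these sizes, and would need only 31 and 28 per group. The printed sample sizes therefore fit a free baseline.

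**Step 2: diet and physical activity (0, 3, 6, 12 months).** Σd² = 0.67375 and (Σd)² = 1.4² = 1.96.
- Free: 0.67375 − 1.96/4 = 0.18375; divided by 0.65 this is 0.2827 per participant per group.
- Constrained: 0.67375 − 0.35 × 1.96/2.05 = 0.33912; divided by 0.65 this is 0.5217.

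| n per group | λ free | λ constrained | Power free | Power constrained |
|---|---|---|---|---|
| 53 | 14.98 | 27.65 | 0.86 | 0.99 |
| 43 | 12.16 | 22.43 | 0.76 | 0.97 |

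Simulation at 53 per group (3000 trials, covariance estimated) gave 0.863 and 0.994. A second simulation (4000 trials), comparing change scores with baseline-adjusted values, gave 0.868 and 0.993, with type I error 0.023 and 0.027.

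**Step 3: SBP, BMI and waist (0, 6, 12 months), borrowing the same effects and correlation.** Σd² = 0.533125 and (Σd)² = 1.025² = 1.050625. At n = 53, λ is 14.91 free and 25.83 constrained, and power is 0.90 versus 0.99. At n = 43 power is 0.81 versus 0.98.

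**Step 4: sensitivity to the correlation, 53 per group, full planned effect**

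| ρ | Diet/activity, free vs constrained | SBP/BMI/waist, free vs constrained |
|---|---|---|
| .35 | 0.86 vs 0.99 | 0.90 vs 0.99 |
| .5 | 0.94 vs 0.995 | 0.96 vs 0.997 |
| .6 | 0.981 vs 0.998 | 0.989 vs 0.999 |

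**Step 5: coaching by time.** The pattern 2 differences are 0.675, 1.375 and 0.80 at 3, 6 and 12 months. Power exceeds 0.999 under both models at 43 and at 53 per group.

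**Step 6: intervals.** For one visit the variance is 2(1 − ρ)/n free and (1 − ρ)(1 + ρ)/n constrained. The ratio of standard errors is √((1 + ρ)/2) = √0.675 = 0.82 at ρ = .35. Visit-specific intervals for genetics and for coaching would be about 18% narrower.

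**The case against.** The strongest reply is that nothing here is wrong. The free-baseline test holds its alpha, it is roughly the test for which 8.1 sized the trial, and at planned enrolment its 0.86 meets the stated .80 to .85. That stands. A reader might infer from 0.86 versus 0.99 that the planned test is invalid or falls short of the plan's target. The documents support neither, because the plan never promised 0.99.

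A reader might also spread the gap over every outcome and both interactions. That does not hold either. Coaching by time has nothing to gain in power. SBP, BMI and waist have fewer visits, and 8.1 gives no effect size or correlation of their own. If they correlate more strongly within person than .35, which the documents do not say, the gain for them is about three points at .5 and one point at .6.

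Third, the free baseline is inferred. Section 8.2 lists the terms but never says that baseline means are free, still names the dropped three-way test, and leaves the type of model open. This is fair. However, the choices it leaves open do not mention baseline handling, and Step 1 shows that the printed sample sizes fit a free baseline.

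Finally, the constraint needs baseline values that assignment has not influenced. Section 5.3.1 describes the blood draw for those randomised to the genetic arms within the same baseline visit as the survey, so the order is unclear. An unconstrained sensitivity fit does not protect against this: if knowing the assignment changes baseline answers, change from baseline is distorted too.

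**Conclusion.** The point holds as lost efficiency in a valid test. For genetics by time on diet and physical activity, using the baseline already collected lifts power from about 0.86 to 0.99 at 53 analysed per group, and from 0.76 to 0.97 at 43. The free-baseline test uses 14.98/27.65, or 54%, of the available noncentrality. For SBP, BMI and waist the corresponding 0.90 versus 0.99 is illustrative only.

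These figures rest on SD 1, compound symmetry, categorical time, the pattern 2 effects and a correlation of .35. With the full planned effect, the gain is under 2 points for both sets of outcomes once the correlation reaches .6, because both powers are near 1. If the true effect were 75% of plan (my assumption; λ is multiplied by 0.5625), diet and activity at 53 per group would show 0.56 versus 0.87 at .35 and 0.82 versus 0.94 at .6.

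For coaching by time the benefit is narrower intervals only. Laboratory values measured at two visits, and the coaching-by-genetics test averaged over visits, are outside this point.

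**What to change.** In 8.2, for diet, physical activity, SBP, BMI and waist, specify one of these:
- a mixed model with categorical time and a common baseline mean across the four groups, with genetics-by-time and coaching-by-time terms at post-baseline visits only; or
- a model for the post-baseline visits with the baseline outcome and baseline-by-visit as covariates.

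In either case, test the genetics effect and the coaching effect jointly over the post-baseline visits at the same .025. Under randomisation this is the same null hypothesis as the interaction test. Write these two-way tests out in place of the three-way interaction that 8.2 still names.

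In 5.3.1, state that the baseline survey and measurements are completed before assignment is disclosed. The unconstrained model may stay as a sensitivity analysis, but it should not be described as a safeguard against baseline values altered by knowledge of assignment.

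The cost is a few sentences in 8.2 and one procedural statement in 5.3.1, which may mean fixing the order of steps at the baseline visit. No added visits, measurements or participants are needed.
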